3.0 Research Goals and Aims

BROAD GOALS OF THE RESEARCH

The goal of this study is to strengthen the **implementation** of a cervical cancer screening service in a decentralized, low-resource area of Senegal naïve to any cancer screening programs by investigating the barriers and facilitators of **initial uptake** and developing and adapting a peer education health promotion intervention to diverse and dynamic contexts to achieve **sustained utilization**.

Through the **SPECIFIC AIMS**, we will

Aim 1: Assess cervical cancer screening access determinants in Kedougou, Senegal by identifying barriers and facilitators of service uptake over time at the person, household, and community levels;

Aim 2: Develop and deploy a wide-reaching, multi-level responsive peer education curriculum aimed at motivating eligible women to seek cervical cancer screenings in Kedougou, Senegal;

Hypothesis: A cervical cancer peer education curriculum developed, implemented, and adapted through a Care Group model will reach 75% of the target audience, improve cervical cancer knowledge, and establish the rate of women and men recommending this screening service to others to 30% over the course of 24 months in the region of Kedougou, Senegal; and

Aim 3: Evaluate the impact of the peer education intervention on initial screening uptake and re-screening rates.

Hypothesis: A context-specific peer education cervical cancer screening curriculum will increase the cervical cancer screening initial uptake rate (first 6 months) in target age women to 35% and will ensure 2 year re-screening rates of 30% in the Kedougou, Senegal study sites.

STUDY DESIGN AND PROCEDURES

[figure not shown]
TABLE 1: Primary Research Questions

AIM	Research Questions
AIM 1	What individual, household, and community factors influence a woman's decision to seek or not to seek cervical cancer screening in Kedougou, Senegal? How do these identified determinants change with time? How does age and gender specifically influence screening program opinions and motivations for screening?
AIM 2	What is the structure, process, and content of a peer education program that empowers eligible women to initially seek cervical cancer screening services in Kedougou, Senegal? What programmatic factors predict the reach and positive reception by a relevant audience of such a health promotion intervention?

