
Recruitment and Enrollment of Participants Followed within Care Groups

We will utilize a random sampling method to select five (5) Care Group Volunteers in the Care Group of each the three (3) sites per cluster. We will seek to enroll, longitudinally follow, and collect data on three (3) younger woman (age 30 to 44) and two (2) older women (age 45 to 59) in each care group over the course of the study. Given that each Care Group has between 8 to 15 volunteers, we are expecting to enroll 1/3 to 1/2 of all Care Group Volunteers across all sites.

Detailed Care Group Volunteer sampling: While visiting a care group meeting, the RA will read the RESEARCH INFORMATION SHEET. The RA will then read the RECRUITMENT SCRIPT and ask the women if they are interested to participate. The RA will record the names of each younger woman (age 30 to 44) who is interested in participating on separate pieces of paper. The RA will fold each piece of paper separately and place into a container. The RA will blindly draw three names. The RA will then record the names of each older woman (age 45 to 59) who is interested in participating on separate pieces of paper. The RA will fold each piece of paper separately and place them into a container. The RA will blindly draw two names. The RA will

read the INFORMED CONSENT and SHORT FORM to each of the chosen participants separately and privately. The RA will obtain participant written consent with the SHORT FORM and will then enroll each participant by entering their contact information in the PARTICIPANT REGISTER. The RA will inform them separately of the data collection schedule.

Recruitment and Enrollment of Participants for Women's Focus Groups

We will conduct two focus groups every six (6) months. Five (5) care group members will be convenience selected from each care group AND two to three (2-3) household women participants will be convenience sampled to participate in a younger women's (age 30 to 49) and an older women's (age 45 to 59) focus group every six (6) months over the course of the study.

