Detailed Women's Focus Group Sampling: Recruiting from Household Participants: The RA will contact enrolled household women participants every six months to convenience sample women for both a Younger and an Older Women's Focus Group. **Younger women's focus group:** The RA will read the FOCUS GROUP RECRUITMENT SCRIPT and ask for interest to participate. The RA will invite the first two to three younger women (age 30 to 44) among those already enrolled in the study who express interest to participate in a focus group. The RA will provide instructions on where and when to go for the focus group. **Older women's focus group:** The RA will read the FOCUS GROUP RECRUITMENT SCRIPT and ask for interest to participate. The RA will invite the first two to three younger women (age 30 to 44) who express interest to participate in a focus group. The RA will provide instructions on where and when to go for the focus group. **Recruiting from Care Group Participants:** The RA will contact Care Group women participants. **Younger women's focus group:** The RA will read the FOCUS GROUP RECRUITMENT SCRIPT and ask for interest to participate. The RA will invite the first two to three younger women (age 30 to 44) among enrolled Care Group participants who express interest to participate in a focus group. The RA will provide instructions on where and when to go for the focus group. **Older women's focus group:** The RA will read the FOCUS GROUP RECRUITMENT SCRIPT and ask for interest to participate. The RA will invite the first two to three younger women (age 30 to 44) who express interest to participate in a focus group. The RA will provide instructions on where and when to go for the focus group. The RA will read the INFORMED CONSENT and SHORT FORM to each of the chosen participants separately and privately. The RA will obtain participant written consent with the SHORT FORM and will then inform them separately of the data collection schedule.

Aim 2: Develop and deploy a peer education curriculum to motivate eligible women to seek screenings. (See Table 3)

TABLE 3: Aim 2 - Peer Education Data Collection

Methodology			Measures	Variables
Quantitative	Document Review DCI: 1611	No human participants. Review of peer education program implementation records.	Program Reach	A. # of individuals, households, communities directly receiving intervention B. # of peer educators C. # of peer education sessions per educator

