There will be two **FGs** (women ages 30 to 44 and ages 45 to 59) per cluster every 6 months throughout the study period. Through FGs we will collect qualitative data, from women stratified by age, which describe demand-side access barriers and facilitators (Table 2). The Senegalese research assistant will moderate the 45 minute FGs in the preferred language (Malinke, Pulaar, or French) and two PCVs will observe and record written observations in real time. We will audio record the sessions (to be transcribed into both French and English). The Research Assistant and PCVs will review the audio record and confirm all notes. The women enrolled as individuals will make of the focus groups. There will be no new women enrolled for this data collection activity.

Aim 2 Focus Groups:

We will conduct two **FGs** per cluster per data collection period for aim 2. Through the FGs we will gather qualitative data that describe the peer educator (matrone and the volunteers from each CG) opinion of the peer education program (Table 3). The CG district coordinators will moderate the 45 minute focus groups in the preferred language (French, Malinke or Pulaar) and two PCVs will observe and record written observations in real time. We will audio record the sessions (and transcribe into French and English). The moderating CG district coordinator and PCVs will review the audio record and confirm all notes.

Participants will include 15 CG volunteers that comprise the FGs in each cluster (no new participants). The women participants are not newly enrolled and are the same as described in the FG activity in Aim 1.

This data collection will occur at baseline and every 6 months during the data collection period. Peace Corps Volunteers will assist the PI and Co-I's in ensuring the fidelity of this data collection.

Document Review – Uptake Data

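### Both recruitment instructions for the older women's focus group invite women aged 30 to 44, and the summary paragraph gives the younger group a range that overlaps the older one

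*Protocol*

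**What the plan says.** The intended strata are given in several places. Section 2.0 (Overview of Study Data Collection) and Table 2 in section 3.0 both divide the women's focus groups into 30 to 44 and 45 to 59. Section 5.0 (Aim 1 Focus Groups) repeats this: "women ages 30 to 44 and ages 45 to 59) per cluster every 6 months".

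The detailed procedure is in section 3.0, Detailed Women's Focus Group Sampling. Its stated purpose is to "convenience sample women for both a Younger and an Older Women's Focus Group". It has four instructions, one for each combination of recruiting stream (household or Care Group) and age group:

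- Younger group, household stream: "The RA will invite the first two to three younger women (age 30 to 44) among those already enrolled in the study".
- Younger group, Care Group stream: "two to three younger women (age 30 to 44) among enrolled Care Group participants who express interest to participate in a focus group".
- Older group, both streams, in identical words: "The RA will invite the first two to three younger women (age 30 to 44) who express interest to participate in a focus group".

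The summary paragraph just before it, under Recruitment and Enrollment of Participants for Women's Focus Groups, describes "younger women's (age 30 to 49) and an older women's (age 45 to 59").

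**The concern.** The detailed procedure is the operative text: it tells the research assistant whom to approach at each six-monthly wave. Under its two older-group headings it names the younger stratum. The summary paragraph has the older range right but the younger range wrong, so neither passage on its own gives a usable rule for both strata.

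This bears on a primary Aim 1 question in Table 1: "How does age and gender specifically influence screening program opinions and motivations for screening". Sections 3.0 and 5.0 say that the women's focus groups collect data stratified by age, and the qualitative analysis in section 6.0 plans to track how age affects opinions. Section 1.0 singles out older women as a high-risk cohort with very low use of the service: of the 509 women screened in 2014, only 10% were 45 or older. An error in recruiting that stratum falls on the women whose views the study particularly needs.

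**Working it through.** There is no sample size or power figure to reproduce. The check sets the statements of the age strata side by side.

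| Place in the protocol | Younger group | Older group |
|---|---|---|
| 2.0, Overview of Study Data Collection | 30–44 | 45–59 |
| 3.0, Table 2 | 30–44 | 45–59 |
| 3.0, Recruitment and Enrollment for Women's Focus Groups (summary) | 30–49 | 45–59 |
| 3.0, Detailed Women's Focus Group Sampling, household stream | 30–44 | 30–44 |
| 3.0, Detailed Women's Focus Group Sampling, Care Group stream | 30–44 | 30–44 |
| 5.0, Aim 1 Focus Groups | 30–44 | 45–59 |

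**Older group.** Four statements give 45–59. Both detailed instructions give 30–44. Of the four detailed instructions, 4 of 4 name 30–44 and 0 of 4 name 45–59. The two ranges share no age, so the literal procedure brings no woman aged 45–59 into the older group from either stream.

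**Younger group.** Only the summary paragraph gives 30–49. Against an older group of 45–59, a woman aged 45 to 49 qualifies for both groups.

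**Groups covered by the faulty sentence.** Section 5.0 gives two Aim 1 groups per cluster per wave, and there are three clusters:

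- Per wave: 2 × 3 = 6 groups, of which 1 × 3 = 3 are older groups.
- Six waves: 3 × 6 = 18 of 6 × 6 = 36.
- Seven waves (baseline plus six further waves over three years): 3 × 7 = 21 of 6 × 7 = 42.

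The number of waves is an assumption. Section 3.0 says six times, but only for the interval interviews. The summary paragraph also omits the words per cluster, so two groups per wave in total is a possible reading of it. The share is one half in every case.

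**Older women reached by other routes.** The enrolment rules in section 3.0 are worded correctly. Five of the ten households per site supply a woman aged 45–59: 5 × 3 sites × 3 clusters = 45. Two Care Group volunteers aged 45–59 per site add 2 × 9 = 18. That makes 63 older women if recruitment is full, using section 3.0's five Care Group women per site (section 4.0 plans 15 per site, a separate discrepancy).

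**Enrolled-only limit.** Both younger-group sentences restrict invitations to women already enrolled; the older-group sentences do not. The household lead-in partly covers this by saying that enrolled women are contacted. Section 5.0 says that no new women are enrolled for this activity.

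**The case against.** The strongest reply is that this is a copying slip which the protocol itself resolves. The faulty sentence sits under an older-group heading, the paragraph opens by naming both groups, and the summary just before it specifies "an older women's (age 45 to 59) focus group every six (6) months over the course of the study". A sensible research assistant would recruit women aged 45 to 59. That stands as to intent: nobody chose to run an older group without older women, and the point is an internal contradiction in the recruitment text. It does not remove the need for correction. The sentence is repeated in both streams, it is the step-by-step instruction, and the nearby summary has an age error of its own.

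Three stronger readings are tempting, and the protocol does not support them.

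- A reader might infer that older women's views vanish from Aim 1, or that the curriculum would be adapted without them. Women aged 45 to 59 are enrolled under correct rules and complete surveys and interval interviews that record age, knowledge, opinions and access concerns. The Aim 2 Care Group focus groups invite all members present, and section 3.0 says the Aim 2 data are used to adapt the intervention.
- A reader might infer that the focus groups are the only qualitative source for Aim 1. Section 5.0 calls the interval interviews semi-structured, while section 3.0 calls the questionnaires close ended, so that cannot be asserted.
- A reader might infer that the field materials carry the error. The focus group recruitment script is a separate document that is not available, and nothing shows what it says.

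**Conclusion.** The recruitment text is wrong as written. Both older-group instructions contradict the 45 to 59 stratum stated in four other places, and the 30 to 49 range in the summary overlaps the older group and conflicts with 30 to 44 elsewhere.

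The consequence is conditional. If the detailed text is followed literally, half of the Aim 1 women's focus groups at each wave are recruited from the wrong stratum, and the age-stratified focus-group comparison is lost. The counts of 18 of 36 or 21 of 42 are the number of groups the sentence covers, assuming two groups per cluster and six or seven waves. They do not estimate how many would actually be misrecruited. Age comparisons from the surveys and interviews would remain possible, and the screening-uptake outcomes are unaffected. It should be corrected, as a small change to an operative instruction.

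**What to change.** In section 3.0, Detailed Women's Focus Group Sampling, change both older-group sentences to invite the first two to three interested women aged 45 to 59 among those already enrolled: household participants in the one stream, Care Group participants in the other. Stating the enrolled-only limit matches the younger-group sentences and section 5.0. In the summary paragraph before it, change the younger range from 30 to 49 to 30 to 44. Then check that the focus group recruitment script uses the same ranges.

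The cost is three wording corrections and one document check. Women aged 45 to 59 are already to be enrolled, so no participants, visits or groups are added.

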4.0 Recruitment, Eligibility and Enrollment

Recruitment

The PI ([name]) and Senegalese Co-I's ([name] and [name]) will train all research assistants, matrones and community health committee leaders at a designated intervention cluster in the Kedougou Region, Senegal. Through our prior work, we have worked directly with each of these individuals. The research assistants, with oversight by the Peace Corps Volunteer research assistants and the Co-I's and PI, will recruit individuals, households, and focus group participants (as described above in section one). The lead Peace Corps Volunteer who is in charge of recruitment, informed consent, participant tracking, and data collection is a UIC MPH trainee (in Senegal as a Peace Corps Volunteer). She is listed as a key personnel on the protocol. These individuals will explain the purpose and activities of the study, and select those who: 1) are confirmed to meet the criteria; and 2) are able to give informed consent. See Inclusion Criteria above.

After the participants give consent, they will participate in the surveys, interviews or focus groups during each data collection period. Drs. [name] and [name] and a Peace Corps Volunteer (MPH level) will oversee preparation of the RA's for the moderation of interviews and focus groups. See detailed description of sources of material.

Human Subjects Involvement and Characteristics.

Throughout this discussion of Human Subjects, "subjects" are referred to as "participants." Inclusion criteria and procedures for each aim of the study are described below.

Determination of Subject Eligibility

The Principal Investigator, Co-Investigators, and onsite Research Personnel will oversee subject eligibility. Eligibility will be determined at the time of recruitment and consent. The Senegalese Co-Investigators ([name], [name]), in collaboration with the U.S. Principal Investigator ([name]) and Project Coordinator, will oversee recruitment. No compensation will be awarded for direct involvement in focus groups or for completion of surveys. However, refreshments may be provided at the time of the focus group. An eligibility checklist in the form of a recruitment script is attached.

Inclusion Criteria

The inclusion criteria are as follows:

Women. Criteria for inclusion include: 1) female Senegal citizen between the ages of 30 and 59, 2) Resident in Kedougou Region, 3) eligible to seek cervical cancer prevention services at a designated health structure in the Kedougou Region, Senegal, 4) willing to participate in survey or interview assessments; and 5) able to give informed consent.

Men. Criteria for inclusion include: 1) male Senegal citizen between the ages of 30 and 59, 2) Resident in Kedougou Region, 3) living in a household with at least one woman eligible to seek cervical cancer prevention services at a designated health structure in the Kedougou Region, Senegal, 4) willing to participate in survey or interview assessments; and 5) able to give informed consent.

Care Group Volunteer. Criteria for inclusion include: 1) Senegal citizen participating as a Care Group volunteer, 2) Resident in the Kedougou Region, Senegal, 3) willing to participate in survey or interview assessments, and 4) able to give informed consent.

Exclusion Criteria

Participants will be excluded if they are

- No additional exclusion criteria exist.

Excluded or Vulnerable Populations

Special considerations of the involvement of women and minorities and the justification of the exclusion of minors are detailed below.

The total planned enrollment / Inclusion of Women and Minorities

1. Planned distribution of participants by sex/gender, race, and ethnicity - The total planned enrollment is:
 - a. Aim 1: 15 women from Care Groups for each site (3) per cluster (3) = 135. Ten women from households for each site (3) per cluster (3) = 90. Ten men from households per site (3) per cluster (3) = 90. This equals a total of 315 individuals (225 women and 90 men). There are no new participants in the focus groups.
 - b. Aim 2: Individual interview (no new participants) + Focus Groups (no new participants) + Document Review (no human participants) = 0 new participants
 - c. Aim 3: Individual interview (no new participants) + Document Review (no human participants) = 0

Total participants = 315

Of these we estimate that there will be 225 women and 90 men. Based on general population numbers for the Kedougou Region in the country of Senegal, we anticipate that 100% of participants will be from African descent. All participants (women and men) will be African and have been included in the "Black" category.

2. Subject selection criteria and rationale for selection –
 - a. No exclusions will be made on the basis of gender for the baseline surveys or longitudinal individual interval interviews described in Aims 1, 2, and 3.
 - b. Men will be excluded from the focus groups (these will be women only) described in Aims 1 and 2.
 - c. No exclusions will be made on the basis of race for all Aims.
3. Rationale for proposed sample –
 - a. The focus groups proposed in Aim 1 and 2 are intended to gather the perspectives of women. Therefore, men will be excluded from participation in this activity.
4. Outreach programs for recruiting
 - a. Males are excluded from the Aim 1&2 focus groups in this study because:
 - i. the research question addressed is relevant to only women;
 - b. No racial and/or ethnic groups or subgroups are excluded from the study

Inclusion of Children.

This study will not involve the recruitment of participants under the age of 30 years. Therefore, no children will be recruited for data collection or involved in the study. The study will focus on the opinions and behaviors of women within the target age range (30 to 59 years old) for cervical cancer screening as stated in the Kedougou, Senegal Cervical Cancer Screening Health Service Regional Guidelines. We will also collect data on men in the corresponding age range (30 to 59 yo).

Sex as a biological variable.

Sex as a biological variable does not apply to this research as the proposed study is not pre-clinical or biomedical research that affects both sexes. Given that cervical cancer affects only women, our principal data collection and investigation will be directed at women within the guideline age range for screening. We will be collecting data from women outside this age range and from men but only to provide perspectives on how affected and targeted women make decisions and to provide insights into how gender and stigma impact decision making in target-age women.^{22,23}

Addressing Gender and Stigma.

Gender roles and stigma are of significant consideration in our proposed research. By investigating the social context of the uptake of this newly implemented cervical cancer screening service we intend to describe as a primary question in aim 1, "How does age and gender specifically influence screening program opinions and motivations for screening?" In addition, in aim 2, we will be collecting data from both men and women describing the number and percent of women and men recommending the service to others. In addition to analyzing the process of a) the role of the social spread of information and b) the value of establishing societal norms (especially among peer groups that don't readily access health services) we intend to provide a deeper understanding on how gender roles in households impact service uptake. We will also describe how social acceptance of a new health service such as cervical cancer screening that has potential stigma considerations (reflecting religious, cultural, or community norms and notions) impact service uptake and sustained utilization.

